### 7.3 **Populations for Analyses**

Set	Description
Randomized	All participants who were randomized.
Modified Intent to Treat (mITT) Set	The mITT set comprises all participants who are randomized, undergo at least 1 pair of PAPs comparison (e.g., CPAP 9 cmH 2 O vs. TPAP), and have at least 1 measurement on the primary endpoint ().
Safety Set	The mITT set comprises all participants who are randomized, undergo at least 1 minute breathing on any TPAP setting.
Per Protocol (PP) Set	The PP Population consists of all participants without any major protocol violations that could influence efficacy assessment.

For the purposes of analysis, the following analysis sets are defined:

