### **Overall Design:**

The TheraPAP Comfort Study is an in-office study to assess comfort of TPAP vs. CPAP in CPAP-naïve patients with OSA during supine wakefulness. Patients will be recruited after routine outpatient visits. They will be asked to breath normally for approximately 1 minute in supine wakefulness while being administered 2 different pressure therapies for comparison. For TPAP therapies, each baseline pressure (9 or 13 cmH2O) will consider 3 separate settings, TPAP A,TPAP B and TPAP C for 9, then TPAP D,TPAP E and TPAP F for 13.

At the first baseline pressure, patients will be asked to choose their preference between CPAP and TPAP A. This will be the primary endpoint. If TPAP A is chosen, testing will move on to the second baseline pressure. If CPAP is preferred, CPAP will then be compared to TPAP B. If TPAP B is chosen, testing will move on to the second baseline pressure. If CPAP is again chosen as preferred, it will be lastly compared to TPAP C, the latter two comparisons being secondary endpoints.

<sup>1 TPAP will be used herein to refer to the actual modified PAP delivery.

At the second baseline pressure, patients will be asked to choose their preference between CPAP and TPAP D. This will be the primary endpoint. If TPAP D is chosen, testing will move on to the second baseline pressure. If CPAP is preferred, CPAP will then be compared to TPAP E. If TPAP E is chosen, testing will move on to the second baseline pressure. If CPAP is again chosen as preferred, it will be lastly compared to TPAP F, the latter two comparisons being secondary endpoints.

Baseline CPAP (cmH2O)	TPAP Setting	Pressure Drop 1 (cmH 2 O)	Pressure Drop 2 (cmH 2 O)
	TPAP A	2	2
9	TPAP B	1	2
	TPAP C	1	1
	TPAP D	2	3
13	TPAP E	2	2
	TPAP F	1	2

**Table 1**. Pressure Drops 1 and 2 refer to the first and the second drops in pressure that occur during inspiration and are maintained until about halfway through expiration. The overall pressure drops consist of Drop 1+ Drop 2. CPAP, continuous positive airway pressure.

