# 2.2.3 Biological Rationale

TPAP is an innovative device/algorithm designed to deliver a lower inspiratory than expiratory PAP. The drop in inspiratory pressure can be modulated during the inspiratory phase. Previous research has shown that reducing inspiratory PAP by placing a resistor in the inspiratory line can enhance subjective comfort and decrease leaks when compared to CPAP, despite maintaining a similar residual apnea-hypopnea index (AHI). However, the resistor could only provide a fixed inspiratory PAP reduction based on existing PAP settings. TPAP addresses this limitation by allowing for adjustable drops in PAP throughout inspiration and part of expiration, offering a potentially more personalized and adaptive therapeutic approach.

	Endpoints
Primary	
 
CPAP vs. TPAP A at 9 cmH2O
 
CPAP vs. TPAP D at 13 cmH2O
 

Secondary	
 
CPAP vs. TPAP B at 9 cmH2O
 
CPAP vs. TPAP C at 9 cmH2O
 
CPAP vs. TPAP E at 9 cmH2O
 
CPAP vs. TPAP F at 9 cmH2O
 

Safety Endpoints	Spontaneous adverse events

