# 4.2.2 In-office study

Individuals who agree to participate will be asked to sign an informed consent prior to commencement of study procedures upon their arrival at the clinic.

The following activities will also occur:

- Height and weight will be measured.
- Randomization of CPAP/TPAP order.

To begin the study, each participant will lay in a supine position on a reclining chair in the office and all therapy comparisons will be made in this orientation. Subsequently, each patient will be studied on two different baseline positive pressures: 9 and 13 cmH2O. At either of the above pressures, each patient will assess CPAP against 2 different pressure drops in one-to-one comparisons.

For the baseline CPAP of 9 cmH2O, TPAP will be set to:

- TPAP A
- Followed by TPAP B if CPAP was previously preferred
- Followed by TPAP C if CPAP was previously preferred

For the baseline CPAP of 13 cmH2O, TPAP will be set to:

- TPAP D
- Followed by TPAP E if CPAP was previously preferred
- Followed by TPAP F if CPAP was previously preferred

Note that TPAP drops, designated as x/y, indicate first and second drop of PAP, starting during inspiration.

Assessment of comfort will be made by comparing one-to-one TPAP against each other or against CPAP by having the patient breathe on the pressure for one minute (or more as needed based on the judgment of the Study Coordinator) and then indicating which is more comfortable

by voice or hand sign. The indicated choice will be recorded by the Study Coordinator. The patient will be able to ask to repeat settings as often as needed to make the most informed choice.

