# 4.2.2.1 Risk-benefit Analysis

The procedures involved in the studies include minimal risk, i.e., related to very short-term TPAP or CPAP administration (e.g., uncomfortable breathing, claustrophobia, lightheadedness, etc.). Upon experiencing any discomfort by the participant, the procedures will be interrupted.

There is no direct benefit or treatment to the participants, however the results of the study can potentially yield future benefit to the participants in terms of wider treatment alternatives for their OSA.

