# 5.8 Stopping Criteria

# 5.8.1 Individual Participant Stopping Criteria

Participants reporting any SAE considered possibly related or related to study device will be withdrawn from the study.

Any other AE that in the judgment of the Investigator necessitates the participant stopping to protect participant safety, will result in early withdrawal from the study.

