# 5.9 Participant Discontinuation/Withdrawal from the Study

A participant may withdraw from the study at any time at his/her own request or may be withdrawn at any time at the discretion of the Investigator for safety, behavioral, or administrative reasons.

If the participant withdraws consent, the Sponsor may retain and continue to use any data collected before such a withdrawal of consent.

All participants who withdraw from the study with an ongoing AE must be followed until the event is resolved or deemed stable.

Participation may be terminated before completing the study and the reason recorded as follows:

- Withdrawal due to AE
- Participant withdrew consent at own request (e.g., due to intolerance to study procedures)
- At the discretion of the Investigator for safety, behavioral, or administrative reasons.
- o Other

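### The Safety Set requires a full minute on TPAP, so participants who withdraw before that minute fall outside the only population defined for safety; the row is also mislabelled as the mITT set

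*Combined protocol and SAP*

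**What the plan says.** The table in section 7.3 defines four sets: Randomized, mITT, Safety and Per Protocol. The text of the Safety Set row is "The mITT set comprises all participants who are randomized, undergo at least 1 minute breathing on any TPAP setting". The row above already defines the mITT set differently, by at least one completed pair comparison and a primary-endpoint measurement.

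The planned exposure per setting is of the same length as the threshold. The synopsis says of participants that "They will be asked to breath normally for approximately 1 minute in supine wakefulness". Section 4.2.2 has each comparison made "by having the patient breathe on the pressure for one minute (or more as needed based on the judgment of the Study Coordinator"), with repeats on request.

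Section 4.2.2.1 describes the risk as "related to very short-term TPAP or CPAP administration" and says "Upon experiencing any discomfort by the participant, the procedures will be interrupted". Section 5.8.1 states: "Participants reporting any SAE considered possibly related or related to study device will be withdrawn from the study". It also provides for withdrawal after any other AE that the Investigator judges to require it. Section 5.9 lists withdrawal due to an AE and, as a separate reason, withdrawal of consent, with intolerance to the procedures as the example.

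The only safety endpoint in Table 3 (section 3) is "Spontaneous adverse events". Section 6.3.1 collects all AEs and SAEs from the start to the end of the study. Appendix 3 records SAEs from randomization, and section 6.2 adds the recording of discontinuations. No section says on which set AEs are summarised.

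**The concern.** A safety population should be fixed by exposure, not by how well the exposure was tolerated. Here membership depends on completing roughly one whole test period in one of the two modes. The risks the protocol names (uncomfortable breathing, claustrophobia, lightheadedness) are acute and could appear within seconds. A participant who withdraws because of such an event before the first TPAP minute is complete is excluded by the event that the set exists to capture.

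The order of CPAP and TPAP is randomised (sections 5.5 and 7.2), so some CPAP-naïve participants meet CPAP first. The synopsis and section 2.1 say that the prototype delivers both modes, and section 4.2.2.1 attaches the risk to both. A participant who withdraws during that first CPAP period has used the study device but cannot enter the set.

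At stake is the summary of the trial's only safety endpoint. Few events are expected, so leaving out a handful of participants with an AE can shift the reported rate.

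**Working it through.** The plan gives no AE rate, early-withdrawal rate or safety calculation, so there is no figure to reproduce. The check is a reading of the rules, followed by an illustration with assumed numbers.

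**Who is in which set**

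- Discomfort, interruption, then resumption and a full minute on any TPAP setting: in the Safety Set. Interruption alone excludes nobody.
- Withdrawal on CPAP after an earlier full TPAP minute: in the Safety Set.
- Withdrawal part-way through a first TPAP period, with no full TPAP minute before it: outside.
- Withdrawal during a first CPAP period: outside.

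The last two groups are in the Randomized set, but the plan gives that set no safety role. Their AEs, SAEs and discontinuations are still collected under sections 6.2 and 6.3.1 and Appendix 3. The mismatch is between collection and the analysis set. Because the synopsis plans only approximately one minute, a strict reading could also exclude a participant whose nominally complete TPAP period ran slightly short.

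**How many might be excluded (rates assumed)**

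Expected number outside = 384 × assumed rate of withdrawal before a full TPAP minute:

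- 1%: 384 × 0.01 = 3.84, about 4
- 2%: 384 × 0.02 = 7.68, about 8
- 5%: 384 × 0.05 = 19.2, about 19

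At a rate of 1%, the chance that at least one participant is excluded is 1 − 0.99^384 = 97.9%.

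**Effect on the AE rate (all inputs assumed except 384)**

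Suppose all 384 planned participants are exposed and 8 inside the set have an AE. Let s be the number who withdraw before a full TPAP minute and a the number of those with an AE.

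- Rate among all exposed = (8 + a)/384
- Rate in the Safety Set = 8/(384 − s)

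| s | a | All exposed | Safety Set | Share of AE participants left out |
|---|---|---|---|---|
| 4 | 0 | 8/384 = 2.08% | 8/380 = 2.11% | 0/8 = 0% |
| 4 | 2 | 10/384 = 2.60% | 2.11% | 2/10 = 20% |
| 4 | 4 | 12/384 = 3.12% | 2.11% | 4/12 = 33% |
| 8 | 0 | 8/384 = 2.08% | 8/376 = 2.13% | 0/8 = 0% |
| 8 | 4 | 12/384 = 3.12% | 2.13% | 4/12 = 33% |
| 8 | 8 | 16/384 = 4.17% | 2.13% | 8/16 = 50% |

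The set understates the rate if (8 + a)/384 > 8/(384 − s). Multiplying out gives a(384 − s) > 8s, that is, a/s > 8/(384 − s). AEs must therefore be more frequent among those excluded than among those in the set. That is plausible where the withdrawal was itself for an AE, and not otherwise.

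**The case against.** Several points on the other side stand.

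- The loss from the reported rate is inferred. The documents do not say that AEs are summarised on the Safety Set, and the Randomized set contains everyone at issue. What is stated outright is the exclusion from the set.
- A reader might infer that an SAE in the first minute would go unrecorded or unreported. It would not. Section 6.3.1 and Appendix 3 require recording and notification to the Sponsor within 24 hours, whatever the analysis set. At most, a summary table omits it.
- A reader might infer that every interruption for discomfort, or every early withdrawal, is a lost AE. Neither follows. A participant who resumes can still qualify, and section 5.9 lists intolerance, behavioral and administrative reasons apart from AEs. Section 5.8.1 covers withdrawal at any time and says nothing about how often it precedes a full TPAP minute.
- The largest contrast in the table needs every one of 8 early withdrawals to have an AE. Section 4.2.2.1 calls the risk minimal, and participation lasts up to half an hour.
- TPAP is the mode under investigation, so restricting a safety population to TPAP-exposed participants can be defended. One prototype delivering both modes, with risk named for both, is a good argument for including CPAP-only participants, but the restriction alone is not plainly an error. The one-minute minimum is the stronger defect.
- A reader might take the row as a second, competing mITT definition. The row is headed as the Safety Set, so a labelling slip is the natural reading.

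None of this removes the exclusion rule, and no other set is assigned to safety.

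**Conclusion.** The point holds in a limited form. The Safety Set row is misnamed, and its one-minute TPAP threshold makes membership depend on tolerating about one full test period. Participants who withdraw for an AE or intolerance before that point, including some who received only CPAP from the study device, are outside the only safety population although their events are collected.

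The documents do not support saying that safety data are lost, that SAE reporting is compromised, or that the AE rate will be understated by a known amount. Understatement requires two things: that AEs are summarised on this set, and that AEs are more frequent among those excluded. The number affected is unknown and probably small. Under the assumed figures, the difference runs from none to about 2 percentage points (4.17% against 2.13%). Preference endpoints are not analysed on this set by anything in the plan. The wording defect is certain and worth correcting because the correction is cheap; its effect on the reported rate is uncertain.

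**What to change.** In the section 7.3 table:

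- Correct the set name in the Safety Set row.
- Remove the one-minute threshold and define the Safety Set as all randomised participants who received any pressure from the TheraPAP device, in either mode and for any duration.
- Add one sentence stating that AEs and discontinuations are summarised on this set.

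Two additions are optional. One is a subset of participants exposed to TPAP for any duration. The other is a tabulation by the mode in use at onset. Because the periods are short and alternate, that tabulation would need a rule for events that begin between or after periods, and the mode at onset would have to be recorded if the form does not already hold it.

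The core change costs one table row and one sentence. It needs no extra participants, visits or procedures and changes no stopping or withdrawal rule. The reported AE rate may be slightly higher.

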# 7.4 Interim Analyses

No interim analysis is planned.

# 8 Supporting Documentation and Operational Considerations

# 8.1 Appendix 1: Regulatory, Ethical, and Study Oversight Considerations

# 8.1.1 Regulatory and Ethical Considerations

This study will be conducted in accordance with the protocol and with:

- Consensus ethical principles derived from international guidelines including the Declaration of Helsinki and Council for International Organizations of Medical Sciences International Ethical Guidelines.
- Applicable International Conference on Harmonization (ICH) Good Clinical Practice (GCP) Guidelines.
- Applicable laws and regulations.

The protocol, protocol amendments, ICF, and other relevant documents (e.g., advertisements) must be submitted to an IRB by the Investigator and reviewed and approved by the IRB before the study is initiated.

Any amendments to the protocol will require IRB approval before implementation of changes made to the study design, except for changes necessary to eliminate an immediate hazard to study participants.

The Investigator will be responsible for the following:

- Providing written summaries of the status of the study to the IRB annually or more frequently in accordance with the requirements, policies, and procedures established by the IRB.
- Notifying the IRB of SAE or other significant safety findings as required by IRB procedures.
- Overall conduct of the study at the site and adherence to requirements of 21 Code of Federal Regulations (CFR), ICH GCP guidelines, the IRB guidelines, and all other applicable local regulations.

# 8.1.2 Financial Disclosure

Investigators will provide the Sponsor with sufficient, accurate information in accordance with local regulations to allow the Sponsor to submit complete and accurate financial certification or disclosure statements to the appropriate regulatory authorities. Investigators are responsible for providing information on financial interests during the course of the study and for 1 year after completion of the study.

# 8.1.3 Informed Consent Process

The Investigator or his/her representative will explain the nature of the study to the participant or his/her legally authorized representative and answer all questions regarding the study.

Participants must be informed that their participation is voluntary. Participants will be required to sign a statement of informed consent that meets the requirements of 21 CFR 50, local regulations, ICH guidelines, Health Insurance Portability and Accountability Act requirements, where applicable, and the IRB.

The medical record must include a statement that written informed consent was obtained before the participant was enrolled in the study and the date the written consent was obtained. The authorized person obtaining the informed consent must also sign the ICF.

Participants must consent to the most current version of the ICF(s) during their participation in the study.

A copy of the signed ICF(s) must be provided to the participant.

If a protocol amendment is required, the ICF may need to be revised to reflect the changes to the protocol. If the ICF is revised, it must be reviewed and approved by the appropriate IEC/IRB and signed by all participants subsequently enrolled in the study.

# 8.1.4 Data Protection

Participants will be assigned a unique identifier by the study site. Any participant records or datasets that are transferred to the Sponsor will contain the identifier only; participant names or any information which would make the participant identifiable will not be transferred.

The participant must be informed that their personal study-related data will be used by the Sponsor in accordance with local data protection law. The level of disclosure must also be explained to the participant.

The participant must be informed that his/her medical records may be examined by Clinical Quality Assurance auditors or other authorized personnel appointed by the Sponsor, by appropriate IRB members, and by inspectors from regulatory authorities.

# 8.1.5 Data Quality Assurance

All participant data relating to the study will be recorded on electronic reports and spreadsheets. Any study data will be de-identified. The Investigator is responsible for verifying that data entries are accurate and correct by physically or electronically signing the study records.

The Investigator must maintain accurate documentation (source data) that supports the information entered in the study records.

The Investigator must permit study-related monitoring, audits, IRB review, and regulatory agency inspections and provide direct access to source data documents.

The Sponsor or designee is responsible for the data management of this study including quality checking of the data.

Records and documents, including signed ICF, pertaining to the conduct of this study must be retained by the Investigator for 5 years after study completion unless local regulations or institutional policies require a longer retention period. No records may be destroyed during the retention period without the written approval of the Sponsor. No records may be transferred to another location or party without written notification to the Sponsor.

All data generated by the site personnel will be captured and stored in an internal passwordprotected system.

# 8.1.6 Source Documents

Source documents provide evidence for the existence of the participant and substantiate the integrity of the data collected. Source documents are filed at the site.

# 8.1.7 Publication Policy

The Sponsor will support publication upon review of the manuscript.

Authorship will be determined by mutual agreement and in line with the International Committee of Medical Journal Editors' authorship requirements.

A summary of the study results will also be posted in a publicly accessible database (e.g., www.ClinTrials.gov).

# 8.1.8 Protocol Approval and Amendment

Before the start of the study, the study protocol and/or other relevant documents will be approved by the IRB/Competent Authorities, in accordance with local legal requirements. The Sponsor must ensure that all ethical and legal requirements have been met before the first participant is enrolled in the study.

This protocol is to be followed exactly. To alter the protocol, amendments must be written, receive approval from the appropriate personnel, and receive IR/Competent Authority approval prior to implementation (if appropriate).

Administrative changes (not affecting the participant benefit/risk ratio) may be made without the need for a formal amendment. All amendments will be distributed to all protocol recipients, with appropriate instructions. Any deviations from the protocol will be reported to the Sponsor as Protocol Deviations.

# 8.1.9 Liability and Insurance

The Sponsor will take out reasonable third-party liability insurance coverage in accordance with all local legal requirements. The civil liability of the Investigator, the persons instructed by him or her and the hospital, practice, or institute in which they are employed and the liability of the Sponsor with respect to financial loss due to personal injury and other damage that may arise as a result of the carrying out of this study are governed by the applicable law.

The Sponsor will arrange for participants participating in this study to be insured against financial loss due to personal injury caused by medical steps taken in the course of the study.

### 8.1.9.1 Access to Source Data

Regulatory authorities of certain countries, IRBs, IECs, and/or the Sponsor's Clinical Quality Assurance Group (or designee) may wish to carry out source data checks and/or on-site audit inspections. Direct access to source data will be required for these inspections and audits; they will be carried out giving due consideration to data protection and medical confidentiality. The Investigator assures the Sponsor and affiliates or designees (such as a CRO) of the necessary support at all times.

